Study Protocol

Protocol Title: Utilization of Confocal Microscopy during Cardiac Surgery

Document Date: October 19, 2018

IRB Approval Date: October 31, 2018

NCT Number: NCT03189134

Utilization of Confocal Microscopy during Cardiac Surgery

A. Specific Aims/Objectives

This is a pilot study, exploring the safety and feasibility of using diluted fluorescein sodium with fiberoptic confocal microscopy during cardiac surgery.

- The primary aim of this study is to evaluate the safety of using diluted fluorescein sodium during cardiac surgery.
- A secondary aim of this study is to evaluate the feasibility of using this imaging modality. Feasibility will be evaluated in two ways: logistically and technologically.
 - Logistical feasibility will be evaluated by measuring increased time on bypass, rate of enrollment, and the ability to incorporate this imaging modality into standard OR procedures.
 - Technological feasibility will center on the ability to capture quality image files. A quality image file is defined as an image file where a rater can visualize the distinguishable features of the tissue type (cardiac tissue, conductive tissue) in order to classify that tissue type correctly.

B. Background and Significance

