The probe will be used in direct contact with the cardiac tissue with a pressure of approximately 0.7 mmHg, which is less than 1% of diastolic blood pressure. The maximum laser energy that the system is capable of delivering is 15 mW at 480 nm. This power and wavelength has been approved by the FDA for direct in-vivo imaging for various body tissues, including gastrointestinal, urogenital, and pulmonary. The proposed application is approximately 80% less than the maximum allowable retinal exposure, according to the IEC 60825-1 standard.

(4) Definition of Primary and Secondary Outcomes/Endpoints

Primary Outcome: All adverse events will be collected and relatedness to study participation will be determined. Complications will be compared to average complication rates for ASD repairs.

Hypothesis: Subjects will not experience a higher rate of adverse events than is expected in a clinical setting (<3-4% for all types of adverse events).

Secondary Outcome: The logistical feasibility of conducting FCM imaging during cardiac surgery.

Hypothesis: The study procedure will be logistically feasible in terms of added time on bypass and the ability to incorporate FCM imaging into standard cardiac surgery OR procedures. The rate of enrollment will be evaluated separately.

Secondary Outcome: The quality of the FCM image files collected, defined as the ability of observers to distinguish features and discriminate between working myocardium and nodal tissue.

Hypothesis: Blinded raters will be able to use the FCM image files to distinguish features and discriminate between working myocardium and nodal tissue.

(5) Data Collection Methods, Assessments, Interventions and Schedule (what assessments performed, how often)

Standardized demographic and clinical assessments of all study participants will be performed via medical record review prior to and after surgery until the subject is discharged from the hospital. Images will be obtained during surgery and saved using Cellvizio Software and Viewer. The image files will be de-identified and provided to blinded raters for analysis. Medical records of enrolled subjects will be reviewed post-surgery while the subject is inpatient in the hospital. Adverse events will be abstracted from the record and recorded on a CRF and input into an InForm database.

(6) Study Timeline

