1. Death. This includes any death that occurs during the conduct of a clinical study, including deaths that appear to be completely unrelated to the test drug (e.g., a car accident). If a study subject dies during the study and an autopsy is performed, the autopsy results will be attached to the study subject's Case Report Form (CRF). Possible evidence of organ toxicity and the potential relationship of the toxicity to the test drug are of particular interest. The autopsy report should distinguish the relationship between the underlying diseases, their side effects, and the cause of death.
2. Life-threatening adverse drug experience. This includes any AE during which the study subject is, in the view of the investigator, at immediate risk of death from the reaction as it occurred. This definition does not include any event that may have caused death if it had occurred in a more serious form. For example, drug-induced hepatitis that resolved without evidence of hepatic failure would not be considered a life-threatening event, even though drug-induced hepatitis can be fatal.
3. Persistent or significant disability or incapacity or substantial disruption of the ability to conduct normal life functions.
4. Inpatient hospitalization or prolongation of existing hospitalization, except for admission for elective surgery.
5. Important medical event that may not result in one of the above outcomes, but may jeopardize the health of the study subject or require medical or surgical intervention to prevent one of the outcomes listed in the above definition of serious event.

(4) Definition of Unexpected Adverse Events

An adverse event is "unexpected" when its nature (specificity) or severity is not consistent with applicable product information, such as safety information provided in the package insert, the investigational plan, the investigator's brochure or the protocol.

In addition, an adverse event is "unexpected" when not one of the most common complications that typically arise post-operation for ASD repair such as: rhythm disturbances, arrhythmia, pericarditis, cardiac tamponade, bleeding, residual holes requiring a re-operation, transfusion associated diseases, stroke, and brain damage. These adverse events will be considered expected and unrelated to the study drug.

(5) Toxicity Grading

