We will assign toxicity grades to indicate the severity of adverse experiences and toxicities. Toxicity grading consistent with NCI-CTCAE v 4.03 will be used for this protocol. The purpose of using the NCI-CTCAE system is to provide standard language to describe toxicities and to facilitate tabulation and analysis of the data and assessment of the clinical significance of treatment-related toxicities.

Adverse events not included in the NCI-CTCAE listing will be recorded and graded 1 to 5 according to the General Grade Definition provided below:

Grade 1	Mild	Transient or mild discomforts (< 48 hours), no or minimal medical intervention/therapy required, hospitalization not necessary (non-prescription or single-use prescription therapy may be employed to relieve symptoms, e.g., aspirin for simple headache, acetaminophen for post-surgical pain).
Grade 2	Moderate	Mild to moderate limitation in activity, some assistance may be needed; no or minimal intervention/therapy required, hospitalization possible.
Grade 3	Severe	Marked limitation in activity, some assistance usually required; medical intervention/therapy required, hospitalization possible.
Grade 4	Life-threatening	Extreme limitation in activity, significant assistance required; significant medical/therapy intervention required, hospitalization, or hospice care probable.
Grade 5	Death	Death

For additional information and a printable version of the NCI-CTCAE v. 4.03 manual, consult the NCI-CTCAE website, <http://ctep.cancer.gov/reporting/ctc.html>.

(6) Guidelines for Determining Causality of an Adverse Event

The Investigator will use the following question when assessing causality of an adverse event to study drug: Is there a reasonable possibility that the drug caused the event? An affirmative answer designates the event as a suspected adverse reaction.

If there is any doubt as to whether a clinical observation is an AE, the event should be reported. All AEs must have their relationship to study product assessed using the terms related or not related. In a clinical trial, the study product must always be suspect. To help assess, the following guidelines are used:

- Related – Related means there is evidence to show a causal relationship between the study product and the adverse event.

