- Possibly Related – There is a reasonable possibility that the study product caused the adverse event. Reasonable possibility means that there is evidence to suggest a causal relationship between the study product and the adverse event.

Specific adverse events considered related or possibly related to study participation have been identified as: myocarditis or ventricular dysfunction, as measured by ejection fraction and fractional shortening. These will be reported to the FDA in an IND Safety Report, per discussion with the FDA.

Specific ECG and rhythm abnormalities requiring DSMB review prior to enrollment of next patient:

1. AV block > the a PR interval > 220 msec lasting more than 2 hours post completion of cardiopulmonary bypass. This does not include transient Wenkebach with sleep/rest/hypothermia.
2. Need for atrial pacing or junctional rhythm lasting more than 6 hours post completion
3. Hypotension or ventricular dysfunction requiring pressor support > 5mcg/kg/min of dopamine more than 4 hours post completion of cardiopulmonary bypass.

- Not Related – There is not a reasonable possibility that the administration of the study product caused the event, and/or there is a more plausible explanation for the adverse event than administration of the study product.

(7) Recording and Reporting Procedures

Reporting Adverse Events and Serious Adverse Events

All AEs will be followed until the time the event is resolved or medically stable, or until subject is discharged from hospital, whichever comes first. AEs may be discovered through any of these methods:

- Observing the subject
- Questioning the subject, which should be done in an objective manner
- Receiving an unsolicited complaint from the subject
- Review of medical records/source documents

All AEs must be recorded accurately on the Adverse Event log for each study subject. The date of onset and duration of the AE, grade, whether it was expected or unexpected, action taken, date of resolution (if applicable) and outcome of the event must be recorded. The investigator will treat subjects experiencing adverse events appropriately and observe them at suitable intervals until their symptoms resolve or their status stabilizes or they are discharged from the hospital.

SAEs and unexpected problems will be reported promptly to BCH IRB according to local regulations and guidelines.

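### Protocol section E(4) rules common surgical complications unrelated to the study drug in advance, while section E(6) requires causality to be assessed for every adverse event

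*Protocol*

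**What the plan says.** Protocol section E(4) (Definition of Unexpected Adverse Events) gives two tests. The first is consistency with product information. Under the second, an event is unexpected if it is not among the "most common complications that typically arise post-operation for ASD repair such as: rhythm disturbances, arrhythmia, pericarditis, cardiac tamponade, bleeding" and the further items that complete the list. The section then rules on the listed events: "These adverse events will be considered expected and unrelated to the study drug".

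Section E(6) (Guidelines for Determining Causality of an Adverse Event) states: "All AEs must have their relationship to study product assessed using the terms related or not related". It adds: "In a clinical trial, the study product must always be suspect". The investigator is to ask, event by event, whether it is reasonably possible that the drug was the cause.

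Section A sets the purpose: "The primary aim of this study is to evaluate the safety of using diluted fluorescein sodium during cardiac surgery". Section D(4) defines the primary outcome in two parts: "All adverse events will be collected and relatedness to study participation will be determined" and "Complications will be compared to average complication rates for ASD repairs".

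**The concern.** Expectedness and causality are different attributes. An event can be a familiar consequence of the operation and still, in a given patient, have been caused or worsened by the study product. E(4) is headed as a definition of the first attribute but also decides the second.

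At stake is the drug-causality record in a study whose first aim is drug safety. The dye is applied directly to the heart, in an operation chosen because it exposes the conduction system, and the two rhythm terms stand at the head of the list declared unrelated. If E(4) is followed, a rhythm event is recorded as unrelated without anyone having asked the E(6) question. If E(6) is followed, the same event gets a real assessment. Two people applying the same protocol could code the same event differently, and both could point to its text.

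**Working it through.** No sample size, rate or error level enters, so there is nothing to compute. The check is a comparison of texts.

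1. **Scope of the E(4) ruling.** The list names nine types: rhythm disturbances, arrhythmia, pericarditis, tamponade, bleeding, residual defects needing re-operation, transfusion-related disease, stroke and brain damage. The first two overlap. The words *such as* leave the list open, within the limit that the complication must be common after ASD repair.

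2. **What the ruling refers to.** The sentence calls its events expected, so it can only mean the listed complications, not the unexpected remainder.

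3. **Scope of E(6).** The duty covers all adverse events. Neither section makes an exception or refers to the other, and E(4) is not worded as a default that an assessment may overturn.

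4. **Side by side, for a listed event:**

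| Question | E(4) | E(6) |
|---|---|---|
| Who decides causality? | The protocol, by event type | The investigator, case by case |
| Starting position | Not the drug | The product is suspect |
| Can the answer be *related*? | No | Yes |

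5. **Link to the primary outcome.** D(4) asks for relatedness to study participation, which is wider than the drug. E(4) therefore presets only the drug component; relatedness to the imaging procedure stays open. The comparison with ASD-repair complication rates uses events whatever their attribution, so no count or rate changes.

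6. **Other safeguards.** Specified rhythm and haemodynamic findings go to the DSMB before the next enrolment (E(6)). Serious events go to the DSMB, whose stated task is their relationship to the underlying disease, and whose panel works with the investigator on whether they are unexpected (E(7)). None of this is stated to be a drug-causality assessment, and the E(7) steps cover serious events only. The items that E(7) requires on the adverse event log include expectedness but do not name relatedness, so the log requirements would not prompt anyone to revisit the E(4) answer.

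7. **Reporting to the FDA.** The expedited route in E(8) needs an event to be serious, unexpected and associated. A listed event fails the last two by definition. The annual route covers serious events that are not associated.

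8. **A preset in the other direction.** E(6) also assigns attribution by type: "Specific adverse events considered related or possibly related to study participation have been identified as: myocarditis or ventricular dysfunction". That rule sends the events to the FDA for scrutiny, whereas the E(4) rule answers the drug question without any. It is not disputed here.

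**The case against.** The strongest defence is that E(4) merely applies in advance the E(6) definition of *not related*, which allows that label where another explanation is more plausible than the product. For common complications of open-heart surgery, the operation usually is the more plausible explanation. But that definition describes the result of weighing a case. It does not permit skipping the weighing, and E(4) leaves no room for the case in which the balance goes the other way.

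Other points on this side carry some weight:

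- **The protocol does not treat causality as closed everywhere.** Where a subject dies and an autopsy is done, E(3) takes particular interest in a possible relationship to the drug. This is true, but it covers only deaths with an autopsy.
- **Expedited reporting would not change.** Listed events stay expected after the fix and so still miss the E(8) expedited test. This stands: what changes is the causality label, not the expedited route.
- **The E(8) gap is not created by E(4).** A serious event that is associated but expected from product information already fits neither route. This also stands. The amendment would bring listed events into that gap, which is why the two sections should be changed together.
- **The study is small and descriptive, and nothing is lost from collection.** This stands and limits the severity.

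**Conclusion.** The contradiction is real and lies in the current text: for a listed complication, E(4) and E(6) cannot both be obeyed. It affects the drug part of the relatedness judgement for nine named types of event and any others read into the open list. It does not affect which events are collected, the comparison with ASD-repair rates, the DSMB holds on enrolment or the transmission of serious events. The number of events concerned among six subjects cannot be derived from the protocol.

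The conclusion assumes only that both sentences are meant as written. A manual of operations or analysis plan not seen here might settle practice, but the protocol would still contain the conflict. The point should be fixed because drug safety is the primary aim and the remedy is short.

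**What to change.** Amend the protocol as follows.

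1. In E(4), delete the words that declare the listed events unrelated to the study drug. Keep the list for expectedness only.
2. State in E(4) or E(6) that every adverse event, listed or not, is assessed case by case for causality under E(6), and that the result is recorded on the adverse event log.
3. In E(8), reword the annual route to cover all serious events not sent by the expedited route. Otherwise a listed serious event judged associated but expected would fit neither route. Leave the E(6) rule on IND Safety Reports for myocarditis and ventricular dysfunction as it is.

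The cost is two or three sentences and a few more causality assessments in six subjects. Some common surgical complications may be coded as possibly related. No treatment rule or analysis count changes.

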Our research team is currently conducting experiments in sheep, but the data have not been published. In these studies, 3 sheep have been anesthetized and placed on cardiopulmonary bypass. Between 5-7mLs of 1:1000 diluted Fluorescite® was applied to the epicardium and endocardium, and images were obtained using the Cellvizio Imaging system. After the images were obtained, the animals were taken off bypass. ECGs were obtained at baseline, after re-perfusing the hearts, and after the animals were taken off bypass. The ECGs confirmed that after the procedure, the hearts resumed normal baseline cardiac activity. Visual examination of the hearts also confirmed normal ventricular function and vigorous activity. Furthermore, preliminary imaging data from these studies confirms that we are able to discriminate conduction tissue from the images taken.

D. Design and Methods

(1) Study Design

We propose a descriptive pilot study to assess the safety and feasibility of using fiber-optic confocal microscopy during cardiac surgery to image the endocardium and epicardium. 6 patients undergoing surgery for closure of atrial septal defect will be enrolled in this study.

All enrolled subjects will receive standard of care for cardiac surgery and the operation will be conducted according to routine procedure. After the sternotomy, the subject will be placed on cardiopulmonary bypass. After cardioplegic infusion and cardiac arrest, the right atrium will be opened to visualize the atrial septal defect.

At this juncture, fluorescein sodium at a concentration of 100ug/ml in sterile saline will be applied topically to the myocardium, where it will diffuse into the endocardium and epicardium. A total volume of 5ml will be applied. The surgeon will confirm there are no visual indicators of an allergic reaction to the fluorescein study drug. As long as there is no appearance of tissue damage, the imaging will proceed. If any signs of allergy or intolerance occur, the dye will be immediately flushed out and no images will be obtained.

The imaging probe of the Cellvizio system will then be applied in direct contact to the region of interest with minimal pressure for approximately 90 seconds. During this period, Cellvizio Software and Viewer will be used to obtain images. The total additional time on bypass will be approximately 3 minutes.

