With several patients eligible weekly, it should be feasible to complete subject recruitment, enrollment, and follow-up within 6 months after study activation. Lead time will be needed to secure FDA and BCH Institutional Review Board (IRB) approval.

E. Adverse Event Criteria and Reporting Procedures

(1) Specification of Safety Parameters

Comprehensive assessments of any apparent toxicity experienced by the study subject will be performed throughout the course of the study. All safety events experienced by study subjects for the duration of the study will be documented. The types of adverse events that must be reported and procedures for appropriately recording, grading and reporting are outlined in this section.

(2) Definition of an Adverse Event (AE) or Medical Event

According to FDA regulations, an adverse event (AE) is any undesirable, noxious, or pathological change compared to preexisting conditions occurring to or in a study subject enrolled in a clinical trial, whether or not the event is considered related to the test drug. This includes the time periods during which no medication is administered to a study subject, such as run-in or follow-up periods. An adverse event is further defined as any change in structure (signs) or function (symptoms) of the body that occurs while the study subject is receiving study drug/placebo. AEs include the following types of changes:

- Suspected adverse drug reactions, which are any adverse events for which there is a reasonable possibility that the drug caused the adverse event. A reasonable possibility implies that there is evidence that the drug caused the event.
- Other medical experiences regardless of their relationship to the test drug, such as injury, surgery, accidents, extensions of symptoms or apparently unrelated illnesses, and significant abnormalities in clinical laboratory values, physiological testing, or physical examination findings.

(3) Definition of Serious Events (Serious Adverse Events, Serious Suspected Adverse Reactions or Serious Adverse Reactions)

A serious adverse event including a serious suspected adverse reaction or serious adverse reaction as determined by the Investigator or the sponsor is any event that results in any of the following outcomes:

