The PI and delegates are responsible for notifying the DSMB chair of all SAEs. DSMB panel will evaluate the relationship of the SAE to the underlying disease. The PI, in cooperation with the DSMB panel, will determine whether the SAE is unexpected in nature and make a recommendation for any further action. The primary consideration is the study subjects' safety.

(8) Regulatory Reporting

The PI will report events that are both serious and unexpected and that are associated with Study Agent/Intervention to the FDA and other applicable health authorities within the required timelines as specified in 21 CFR 312.32: fatal and life threatening events within 7 calendar days (by phone /fax/electronic communication) and all other serious adverse events in writing within 15 calendar days. All serious events designed as "not associated" to Study Agent/Intervention, will be reported to the FDA at least annually.

Given the low dose and method of delivery of fluorescein sodium, serious adverse events related to the study drug are not anticipated. Subjects will be monitored at the time of dye application to observe for signs of allergy or intolerance. If any signs of allergy or intolerance occur (as evidenced by discoloration of tissue or other signs of allergic reaction), the dye will be immediately flushed out and no images will be obtained. As per standard of care for patients undergoing cardiac surgery, subjects will receive an intraoperative echocardiogram after being separated from bypass, and will be monitored closely post-surgery. Before being discharged, all subjects will receive an electrocardiogram and trans-thoracic echocardiogram, in accordance with standard of care.

F. Data Management Methods

Study specific case report forms (CRFs) will be completed and the case report forms will be stored in individual subject binders. Data will be transcribed to a secure research data management system (InForm database). All hardcopies will be kept in a locked file cabinet accessible by authorized study staff only. Subject confidentiality will be maintained by recording subject data using a unique subject identifier. Identifiable linking data, such as contact information and medical record numbers, will be recorded and stored separately from the clinical study data.

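### The only haemodynamic trigger for a DSMB hold is written as a dopamine rate, so comparable support with another agent does not, on its wording, stop the next enrolment

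*Protocol*

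**What the plan says.** Section E(6) of the protocol introduces a short list with "Specific ECG and rhythm abnormalities requiring DSMB review prior to enrollment of next patient". The first item is AV block defined by a PR interval above 220 msec for more than 2 hours after bypass. The second is a need for atrial pacing, or junctional rhythm, for more than 6 hours. The third is haemodynamic: "Hypotension or ventricular dysfunction requiring pressor support > 5mcg/kg/min of dopamine more than 4 hours post completion of cardiopulmonary bypass".

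The protocol does not prescribe a vasoactive regimen. Section D(1) states: "All enrolled subjects will receive standard of care for cardiac surgery and the operation will be conducted according to routine procedure".

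Three other provisions could pick up the same event:

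- Section E(7), adverse event log: "All AEs must be recorded accurately on the Adverse Event log for each study subject".
- Section E(7), serious events: "The PI and delegates are responsible for notifying the DSMB chair of all SAEs". The investigator, together with the DSMB, "will determine whether the SAE is unexpected in nature and make a recommendation for any further action".
- Section E(6), for myocarditis or ventricular dysfunction: "These will be reported to the FDA in an IND Safety Report, per discussion with the FDA".

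**The concern.** The first two triggers describe the patient's condition or need. The third describes it through the infusion rate of one named drug. If the team supports the circulation with something else, the severity of the event no longer decides whether the trigger is met.

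This matters because safety is the primary aim and the hold is the protocol's only stated rule that makes the next subject wait. The events concerned are also ones the protocol itself has in view: section E(6) names ventricular dysfunction in advance as related or possibly related to participation, and section C lists transient hypotension among the reactions reported with intravenous fluorescein.

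**Working it through.** There is no figure in the plan to reproduce. The values 5 mcg/kg/min and 4 hours are thresholds that the protocol sets. The check applies the wording to plausible cases and then asks whether another provision would impose the same hold.

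**Literal test.** Trigger 3 is met if hypotension or ventricular dysfunction is present, the dopamine rate exceeds 5 mcg/kg/min, and the time since bypass exceeds 4 hours. Suppose the first and third conditions are satisfied.

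| Support beyond 4 hours | Dopamine test | Hold required? |
|---|---|---|
| Dopamine above 5 mcg/kg/min | true | yes |
| Another agent alone, any dose | 0 > 5: false | no |
| Dopamine at 5 mcg/kg/min plus a second agent | 5 > 5: false | no |

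**Search for a wider rule.** Dopamine is the only vasoactive drug named in the protocol. There is no clause for equivalents, no list of other agents and no conversion.

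**Other routes compared with the hold.**

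| Route | Covers the event? | Makes the next enrolment wait? |
|---|---|---|
| AE log, E(7) | yes | not stated |
| SAE notice to the DSMB chair, E(7) | only if judged serious under E(3) | not stated; leads to a recommendation |
| IND Safety Report, E(6) | ventricular dysfunction, not hypotension alone | not stated |
| Triggers 1 and 2, E(6) | only if a conduction or rhythm problem coexists | yes |

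Seriousness can turn on judgement here. The subject is already an inpatient, with an expected stay of 3 to 5 days (section D(1)). An episode that neither threatens life nor prolongs the stay would qualify mainly as an important medical event under item 5 of E(3).

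**Exposure.** With 6 subjects (sections D(1) and J), an event in subject k leaves 6 − k still to enrol: 5, 4, 3, 2, 1 and 0 for k = 1 to 6. This is the upper limit on later enrolments made without the mandatory review. Section D(6) describes the flow as "With several patients eligible weekly", so a next candidate may be available before any review that is not tied to enrolment.

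**The case against.** The strongest reply is that the trigger is based on need. It speaks of a state that requires support above a level, and dopamine is merely the unit in which that level is expressed; a clinician would count heavy support with another drug as exceeding it. That reading is possible, but the protocol does not state it and gives no conversion. It could not be applied consistently, and enrolling the next patient on the literal reading would not breach the protocol.

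Second, most of the gap is covered elsewhere. Prolonged support of this order is a strong candidate for an SAE, and the DSMB's advice could include a pause. This stands as mitigation: no safety data are lost, and what remains is mainly events judged non-serious. It does not replace a hold that the protocol chose to write in addition to these routes.

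Third, an equivalence might sit in the planned manual of operations (section G). That document is not available here and cannot be assumed to widen a rule fixed in the protocol.

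Fourth, eligible patients are not enrolled patients. Section D(6) allows 6 months, which is 6 / 6 = 1 subject a month if the whole window is used, and two-parent consent slows uptake. This is fair. It makes it less likely that the next enrolment comes before an SAE review, but an event judged non-serious prompts no DSMB notice under section E(7) at all.

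Finally, the size is unquantified, and if dopamine is the site's usual agent the practical effect is small. That also stands.

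**Conclusion.** The concern holds on the wording. One of the three hold triggers, and the only haemodynamic one, depends on the drug chosen and not on the degree of support. The consequence is that DSMB review is not mandatory before the next enrolment, for up to 6 − k later subjects; the upper end of 5 assumes an event in the first subject and no voluntary pause by the investigator or the DSMB thereafter.

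The share of supported subjects managed on agents other than dopamine is not given. It could lie anywhere from 0 to 1, near 0 if dopamine is routine at the site, so no frequency is claimed. No endpoint or analysis is affected. The rule should be corrected because it is a safety rule drawn too narrowly, with partial cover from the SAE and FDA routes.

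**What to change.** Amend the third trigger in section E(6) in two places. Let it refer to pressor *or inotropic* support, and after the dopamine threshold add: *or equivalent support with any other vasoactive or inotropic agent, alone or in combination*. Leave the 4-hour limit as it is. Agree with the DSMB, before the first patient, what counts as equivalent, and record it where the clinical team will use it.

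The cost is one reworded line and a short agreed equivalence. The downside is possibly an extra DSMB review before an enrolment.
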